6.9 Visit 7 - Final Restoration

Subjects will be recalled at 10 weeks (± 2 weeks) post loading to seat the final restoration.

The subject will have the following procedures and/or evaluations performed and documented:

- · Permanent prosthesis seated
- Oral hygiene evaluation
- Concomitant medication
- Adverse event check
- Implant stability by RFA
- Implant survival
- Soft tissue evaluation
- Intra-oral photographs

6.10 Visit 8 – 6 Month Follow-Up

Subjects will be recalled at 6 months (± 1 month) for brief evaluation of the implant supported final restoration and check possible adverse events.

- Oral hygiene evaluation
- Concomitant medication
- Adverse event check
- Implant survival
- Intra-oral photographs

6.11 Visit 9 – 12 Month Follow-Up

Subjects will be recalled at 12 months (± 1 month). Primary and secondary endpoints will be evaluated at this visit.

Periodontal measurements (PPD and mSBI at adjacent teeth)

- Oral hygiene evaluation
- Concomitant mediation
- Adverse event check
- Verbal confirmation of pregnancy status, if applicable
- Standardized periapical radiograph
- CBCT localized
- Implant survival and success
- Soft tissue evaluation (gingival margin and papilla height)
- Subject satisfaction
- Intra-oral photographs

6.12 Visits 10, 11, 12, and 13 - Follow-Up Visits

Subjects will be recalled at 24 months (± 1 month), 36 months (± 1 month), 48 months (± 1 month), and 60 months (± 1 month) post loading. Data from these visits will be used for the additional analyses.

- Periodontal measurements (PPD and mSBI at adjacent teeth)
- Oral hygiene evaluation
- Concomitant mediation
- Adverse event check
- Verbal confirmation of pregnancy status, if applicable
- Standardized periapical radiograph
- CBCT localized

- · Implant survival and success
- Soft tissue evaluation (gingival margin and papilla height)
- Subject satisfaction
- Intra-oral photographs

7 Evaluation of Adverse Events

For the avoidance of doubt, *all* AE/SAEs as defined below, **regardless of whether they are related to the investigational device**, should be collected, fully investigated and documented in the source document and appropriate case report form for all subjects from the time of the signing of the informed consent until the last protocol-specific procedure. Documentation includes dates of event, treatment, outcome, assessment of seriousness and causal relationship to the device and/or study procedure (rationale to be provided).

7.1 Definitions

7.1.1 Adverse Event (AE)

An AE is defined as any untoward medical occurrence, unintended disease or injury, or any untoward clinical signs (including abnormal laboratory findings) in subjects, users or other persons, whether or not related to the investigational medical device. This definition includes events related to the investigational medical device or the comparator, or events related to the procedures involved. For users or other persons, this definition is restricted to events related to investigational medical devices.

7.1.2 Serious Adverse Event (SAE)

Any adverse event that:

- led to a death
- led to a serious deterioration in the health of the subject, that either resulted in
 - o a life-threatening illness or injury, or
 - o a permanent impairment of a body structure or a body function, or
 - o in-patient or prolonged hospitalization, or

- medical or surgical intervention to prevent life-threatening illness or injury or permanent impairment to a body structure or a body function,
- led to fetal distress, fetal death, or a congenital abnormality or birth defect

NOTE: A planned hospitalization for a pre-existing condition, or a procedure required by the protocol, without serious deterioration in health, is not considered to be a serious adverse event.

7.1.3 Device Deficiency (DD)

A device deficiency is an inadequacy of a medical device with respect to its identity, quality, durability, reliability, safety or performance. DDs include malfunctions, use errors and inadequate labeling.

7.1.4 Adverse Device Effect (ADE)

An ADE is an adverse event related to the use of an investigational medical device. This definition includes adverse events resulting from insufficient or inadequate instructions for use, deployment, implantation, installation, or operation, or any malfunction of the investigational medical device. This definition includes any event resulting from use error or from intentional misuse of the investigational medical device. Any adverse event which the clinical investigator believes has even a possible relationship to the device will be classified as an ADE.

7.1.5 Serious Adverse Device Effect (SADE)

An SADE is an adverse device effect that has resulted in any of the consequences characteristic of a serious adverse event.

7.1.6 Unanticipated Serious Adverse Device Effect (USADE)

An USADE is a serious adverse device effect which by its nature, incidence, severity or outcome has not been identified in the current version of the risk analysis report.

7.1.7 Anticipated Serious Adverse Device Effect (ASADE)

An ASADE is a serious adverse device effect which by its nature, incidence, severity or outcome has been identified in the risk analysis report.

Summary of the classification for adverse events:

Adverse events	Non-device related	Device or procedure related Adverse Device Effect (ADE)	
Non-serious	Adverse Event (AE)		
	Serious Adverse Event (SAE)	Serious Adverse Device Effect (SADE)	
Serious		Anticipated Anticipated Serious Adverse Device Effect (ASADE)	Unanticipated Unanticipated Serious Adverse Device Effect (USADE)

7.2 Assessment of Adverse Events

In the event of an adverse event, the investigator or another suitably qualified clinician who is trained in recording and reporting AEs and have been delegated to this role (such delegation must be captured in the study site delegation log) must review all documentation (e.g., hospital notes, laboratory and diagnostic reports) relevant to the event. Each adverse event should be assessed for seriousness, relationship to the study device or the procedure, severity, outcome, and expectedness, as described below, by the Investigator.

7.2.1 Seriousness

An adverse event will be described as serious if it meets the definition in Section 7.1.2. The rationale for the assessment shall be provided in a short narrative.

7.2.2 Relationship to the Study Device

The investigator should assess the relationship of the adverse event to the implanted product (e.g., dental implant) and provide the rationale in a short narrative. The relationship should be assessed using the following categories:

 Definitely related – There is a reasonable causal and temporal relationship between the treatment with the study device and the adverse event.

- Possibly related The causal and temporal relationship between the treatment with the study device and the adverse event is less likely; however, the determination that there is no relationship cannot be made.
- Not related A causal relationship with device application can be definitely
 excluded. By definition, all AEs/ADEs, with a start date before the surgery
 procedure at Visit 2 must be assigned a "not related" relationship with study
 device.

NOTE: Device deficiencies that might have led to an SAE are always related to the medical device.

7.2.3 Relationship to the Procedure

The investigator should assess the relationship of the adverse event to the implant procedure (e.g. placement of dental implant) and provide the rationale in a short narrative. The relationship should be assessed using the categories described in Section 7.2.2.

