8.1 Relationship to Study Device or Procedure

The causal relationship between the adverse event and the study device or procedure will be defined as follows:

- Definitely related: Reasonable causal and temporal relationship
- Possibly related: Causal and temporal relationship is less likely; however, the determination that there is no relationship cannot be made
- Not related: Causal relationship can be definitely excluded

For purposes of dichotomizing the causal relationship in safety summaries, events that are "Definitely related" or "Possibly related" will be considered related.

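### Because procedure-relatedness is judged against implant placement only, the same extraction or graft complication can be coded as an adverse device effect in the test arm and as a plain adverse event in the control arm

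*Protocol*

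**What the plan says.** Relatedness is assessed on two axes. For the device, Protocol 7.2.2 says: "The investigator should assess the relationship of the adverse event to the implanted product (e.g., dental implant". For the procedure, Protocol 7.2.3 says: "The investigator should assess the relationship of the adverse event to the implant procedure (e.g. placement of dental implant". Both use the same three categories. An event is not related only if a causal link can be definitely excluded; if it cannot be excluded, the event is possibly related. Protocol 7.1.4 adds: "Any adverse event which the clinical investigator believes has even a possible relationship to the device will be classified as an ADE". SAP 8.1 counts definite and possible links alike as related.

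The texts disagree or are incomplete in three places:

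- **What an ADE is.** Protocol 7.1.4 ties it to the device. The summary table in Protocol 7.1.7 heads the column "Device or procedure related Adverse Device Effect (ADE".
- **What the procedure is.** The introduction to Protocol section 7 asks for "causal relationship to the device and/or study procedure (rationale to be provided". Protocol 7.2.3 and 8.4.4 narrow this to the implant procedure. SAP 8 and 8.1 say only *procedure*, without defining it.
- **Which visit.** Protocol 7.2.2 requires a finding of not related to the device for "all AEs/ADEs, with a start date before the surgery" at Visit 2. The schedule has only Visits 2a and 2b.

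On timing (Protocol 3.3, 6.1, 6.4), test subjects have extraction, graft and implant in one session. Control subjects have extraction and graft at Visit 2a and the implant at 17 ± 1 weeks. The current protocol requires the graft in both arms (5.2.3). SAP 10.3.2 records that protocol version 2 stated no such requirement.

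ADE incidence is a secondary endpoint (Protocol 3.5) and a safety endpoint (SAP 4.4). Adverse events are among the outcomes to be compared between arms (SAP 3). The safety analysis is descriptive, without testing (SAP 8).

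**The concern.** Every subject has an extraction, and under the current protocol every subject has a socket graft. Pain, swelling, bruising or infection after that step is a plausible event in either arm. The list of expected ADEs in Protocol 7.2.6 contains just such general post-surgical signs: bruising is rated frequent, and pain, swelling and redness probable. In a test subject the socket already holds an implant, so the investigator can rarely exclude a link. In a control subject at the same stage there is no implant to link to.

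If the two arms classify the same complication differently, the ADE table by arm mixes a real effect of placement timing with an effect of the coding rule. The person who judges relatedness also knows the arm, because the study is not blinded (Protocol 5.2.2). A descriptive table is still read as a comparison. One of the trial's stated purposes is to inform clinicians on the timing of placement.

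**Working it through.** **Step 1. One event traced through the rules.** Take a socket infection that starts one week after extraction.

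| Rule | Test arm | Control arm |
|---|---|---|
| Implant in place at onset | Yes, same session | No, due at 17 ± 1 weeks |
| Device relation (7.2.2) | Hard to exclude, so at least possible | None |
| Procedure relation, narrow wording (7.2.3, 8.4.4) | At least possible | None; implant surgery has not happened |
| Procedure relation, wide wording (section 7 introduction) | At least possible | Can be related |
| ADE under 7.1.4 | Yes | No, under either procedure wording |
| ADE under the 7.1.7 table | Yes | Only under the wide wording |

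Two ADE definitions and two procedure wordings give four readings. Coding is the same in both arms under only one of them (the 7.1.7 table with the wide wording); under the other three it differs. The unclear Visit 2 does not change this. If it means 2b, the start-date rule forces the control event to not related to the device; if it means 2a, the absence of a device gives the same answer. The asymmetry concerns events with onset before the control arm's implant surgery.

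**Step 2. Size.** The plan states no ADE rate and no sample size for safety, so there is no figure to reproduce. Inputs:

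- 26 per arm: 52 subjects at 1:1 (Protocol 3.7). The SAP reports 53 randomised, which changes nothing material.
- Assumed, not in the documents: implant-related risk p_i = 10–20%; extraction/graft complication risk p_e = 5–20%; share of the latter called at least possibly related in the test arm r = 0.25–1. True risks are equal in both arms and independent.

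Test: P_T = 1 − (1 − p_i)(1 − r·p_e). Control: P_C = p_i. Difference due to coding: D = (1 − p_i)·r·p_e.

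| p_i | p_e | r | P_T | P_C | D (points) | Subjects of 26 |
|---|---|---|---|---|---|---|
| 20% | 5% | 0.25 | 21.0% | 20% | 1.0 | 0.26 |
| 10% | 10% | 0.5 | 14.5% | 10% | 4.5 | 1.17 |
| 10% | 20% | 0.5 | 19.0% | 10% | 9.0 | 2.34 |
| 20% | 20% | 1 | 36.0% | 20% | 16.0 | 4.16 |
| 10% | 20% | 1 | 28.0% | 10% | 18.0 | 4.68 |

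The first and last rows are the extremes: 0.8 × 0.25 × 0.05 = 0.010 and 0.9 × 1 × 0.20 = 0.180.

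**Step 3. Same rule in both arms.** If all extraction/graft events count, both arms show 1 − (1 − p_i)(1 − p_e), which runs from 14.5% (10%, 5%) to 36% (20%, 20%). If none count, both show p_i. The difference is 0 either way.

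**Step 4. Does this fix the net direction?** No.

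- Control subjects have a separate implant operation, and all of its events count. If its risk were 1 − (1 − p_i)(1 − r·p_e) rather than p_i, for example 28% instead of 10% in the last row, the coded arms would be equal.
- Suppose instead that each surgical session carries risk s, assumed 20% (range 10–40%), and all test-arm events are called related. Coded ADEs are then 20% in both arms. Counting every procedure gives 20% in test and 1 − 0.8² = 36% in control (10% v 19% to 40% v 64% over the range). Here the coding hides a difference in favour of the test arm.

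Under both models the coding moves the comparison against the test arm, relative to counting all procedures. What the table would finally show depends on inputs that the documents do not give.

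**The case against.** The strongest reply is that an event before any implant is placed is not a device effect, so leaving it out of the control arm's ADEs is simply correct. Device-relatedness is assessed separately in 7.2.2, and 7.1.4 rests on that axis alone. The introduction to section 7 asks about the study procedure, and the SAP, which prevails in a discrepancy (SAP 1), does not restrict *procedure* to implant placement. A control extraction event could therefore be coded procedure-related. All AEs are collected from consent in both arms, so control complications remain visible. Nothing is tested, and study success rests on bone level alone (SAP 2.4).

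Much of this stands. Relatedness as a whole is not judged only against the implant procedure; the narrowing applies to the procedure axis. Total AE incidence is not distorted.

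It does not remove the point. Excluding pre-implant events from control ADEs is right in itself, but the equivalent test-arm events stay in. The SAP's wider word carries no definition, while the instruction that investigators follow when they code (7.2.3) and the protocol's own safety analysis (8.4.4) use the narrow one.

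A reader might infer that the ADE comparison is built to disfavour immediate placement. Nothing in the documents shows intent, and the control arm's second operation counts in full.

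**Conclusion.** The rules as written allow the same extraction or socket-graft complication to be an ADE in the test arm and a plain AE in the control arm. For those events the coding tends to count against immediate placement. Under the assumed rates, the artefact is about 1 to 18 percentage points, or 0.3 to 4.7 subjects of 26.

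That range rests wholly on assumed rates, independence, and equal true risks in the two arms. A figure such as 28% v 10% should not be read as an estimate: it is the top of the range and needs every test-arm extraction or graft event to be called related. Neither the size nor the sign of the net ADE difference follows from the documents.

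The primary endpoint and total AE counts are unaffected. The graft part applies with certainty only to subjects enrolled under protocol version 3 (cohort 2 in SAP 10.3.2); the extraction part applies to all. This is a cheap improvement to a secondary comparison and does not threaten the trial's main conclusion.

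**What to change.** 1. Record relatedness in two separate categories in both arms: to extraction and socket grafting (Visit 2a), and to implant placement (Visit 2b).
2. State in Protocol 7.2.2 whether Visit 2 means 2a or 2b.
3. Reconcile Protocol 7.1.4 with the 7.1.7 table on whether an event related only to a procedure is an ADE. Use one term, with a definition, in place of the differing procedure wordings in the section 7 introduction, 7.2.3, 8.4.4 and SAP 8.1.
4. In SAP 8, tabulate by arm all events related to the device or any study procedure from Visit 2a, split by onset before or after implant placement. Show device-related ADEs separately, with a note that in the test arm they cannot be separated from extraction.

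The cost is one case report form field, or a recoding of existing records, plus one table. Event dates and relatedness narratives are already required, and SAP 10.6 gives the amendment route.

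There are two drawbacks. The control arm's related-event count will rise because it has two operations, and the table should say so. Any retrospective recoding would be open label, and 46 subjects had already completed the 12-month visit when the SAP was written. The split by onset date needs no recoding, so it should be shown alongside.

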7.2.4 Severity

Each adverse event should be assessed by the investigator for its severity, or the intensity of an event experienced by a subject, using the following:

- Mild discomfort noticed, but no disruption in daily activities; the event is easily tolerated by the subject
- Moderate discomfort sufficient enough to reduce or affect normal daily activity
- Severe Inability to work or perform normal daily activity and/or the subject's life is at risk from the adverse event

The maximum severity observed is to be recorded, except if there is a significant worsening in an AE/ADE severity after device intake, then the change will be tracked as a new AE/ADE record as follows:

- The same wording describing the original AE/ADE must be used.
- Outcome of the initial entry should be designated as 'worsened'.

 The end date of the previous AE/ADE must equal the start date of the new AE/ADE.

7.2.5 Outcome

The outcome should reflect the status of the adverse event at the moment of recording.

- Resolved The subject fully recovered from the event without any sequelae.
 This option also applies when it is unknown whether there are sequelae.
- Resolved with sequelae The subject's condition stabilized despite the
 persistence of sequelae (e.g., lesion or medical condition which is a
 consequence of the event). This option does not apply to irreversible
 congenital anomalies (see under "ongoing").
- Ongoing The subject has not yet recovered from the event. By convention, in the case of an irreversible congenital anomaly, the "Ongoing" option should be chosen and understood as "Not recovered/Not resolved". The same applies to conditions that are not yet resolved, but are controlled by medication (e.g., diabetes, epilepsy) and therefore may not have any symptoms.
- Worsened The severity of the AE/ADE increased.
- Fatal The event is related to a death; whether it caused death or contributed to it. If the subject died of a different cause, prior to resolution of the AE/ADE, the outcome of this AE/ADE should designated "Ongoing", and not "Fatal", and an end date should not be specified.
- **Unknown:** Knowledge of the current status of the AE/ADE is truly not available to the investigator (i.e. event was ongoing at last observation, but no further contact with the subject could be established). However, all efforts should be made to determine the outcome of any AE, especially that of an SAE/SADE.

7.2.6 Expectedness

If the adverse event is judged to be related to the device, the investigator will make an assessment of expectedness based on knowledge of the reaction and any relevant product information as documented in the IFU and current protocol. The event will be classed as either;

- **Expected**: the reaction is consistent with the effects of the device listed in the IFU and protocol;
- **Unexpected**: the reaction is not consistent with the effects listed in the IFU and protocol.

The table below presents the potential expected adverse device effects following the insertion of dental implants.

Table: List of expected ADEs following the insertion of dental implants:

Biological complications			
Nature of effect	Severity (mild, moderate, severe)	Frequency (very rare, rare, probable, frequent)	
Peri-implant mucositis			
Bleeding (BOP Bleeding On Probing)	mild	probable	
Bruising	mild	frequent	
Delayed healing of the gum	mild	rare	
Inflammatory papillary hyperplasia	mild	probable	
Gingival/mucosal hyperplasia	mild	probable	
Pain	mild to moderate	probable	
Recession/dehiscence of the gum	moderate	rare	
Redness	mild	probable	
Suppuration	moderate	probable	
Swelling/gingival inflammation	mild	probable	
Peri-implantitis		And Andrews Control of the Control o	
Bleeding (BOP Bleeding On Probing)	mild	probable	
Bone loss around implant	moderate	probable	
Bruising	mild	frequent	
Infection at implant site without suppuration (not recurrent)	mild to moderate	probable	
Infection at implant site with suppuration (not recurrent)	moderate	rare	
Recurrent infection at implant site without suppuration	moderate to severe	rare	

Recurrent infection at implant site with suppuration	moderate to severe	rare
Systemic infection	severe	very rare
Pain	mild to moderate	probable
Swelling	mild	probable
Bone integration deficiency		L'
Early loss/exfoliation (within 2 weeks after surgery)	moderate	probable
Late loss/exfoliation (after prosthetic restoration)	moderate	probable
No primary stability (at surgery)	moderate	rare to probable
Implant mobility (tactile horizontal or vertical)	moderate	rare to probable
Radiolucency	mild to moderate	probable
Aspiration of implant	severe	very rare
Swallowing of implant	severe	very rare
Non-plaque related	7	
Chronic pain in connection with the dental implant	mild to moderate	rare
Foreign body sensation	mild	probable
Material allergy	moderate	rare
Oro-sinus or oro-nasal intrusion/fistula	severe	very rare
Permanent paresthesia, dysesthesia	severe	rare
Temporary or permanent nerve damage in the jaw	severe	very rare
Mechanical complications		
Nature of effect	Severity (mild, moderate, severe)	Frequency (very rare, rare, probable, frequent)
Loosening of abutment screw	mild	probable
Loosening of an healing cap	mild	probable
Loosening of prosthetic screw	mild	probable
Lost/failure of an abutment	moderate	probable
Lost/failure of an healing cap	mild	probable
Fracture of abutment screw	moderate	probable

Fracture of prosthetic screw	mild	probable	
Fracture of implant	moderate	rare	
Technical complications			
Nature of effect	Severity (mild, moderate, severe)	Frequency (very rare, rare, probable, frequent)	
Failure of prosthesis (framework, opposing framework)	moderate	rare	
Fracture of prosthesis	mild to moderate	probable	
Fracture of veneering material	mild	probable	
Irreversible damage to adjacent/opposing teeth	moderate	rare	
Loss of cement retention of prosthesis	mild	probable	
Other complications			
Nature of effect	Severity (mild, moderate, severe)	Frequency (very rare, rare, probable, frequent)	
Aesthetic problem	mild	rare	
Aspiration of component(s) (other than implant)	severe	very rare	
Jaw, bone fracture	moderate to severe	very rare	
Phonetic difficulties	mild to moderate	rare	
Swallowing of component(s) (other than implant)	severe	very rare	
Hypersensitivity (adjacent teeth)	mild	probable	

